## **7.7 EXTENT OF EXPOSURE**

Since only a single dose is administered per subject, a listing will be sufficient to give account of the extent of exposure.

## **7.8 SAFETY ANALYSIS**

All safety analyses will be performed on the TS.

### **7.8.1 Adverse Events**

AEs will be coded with the most recent version of MedDRA at database lock.

The analyses of AEs will be descriptive in nature. For further details on summarisation of AE data, please refer to “Analysis and Presentation of AE data from clinical trials” (9) and “Handling of missing and incomplete AE Dates” (3).

#### **Section 7.2.5 of the CTP:**

*Statistical analysis and reporting of adverse events will concentrate on treatment-emergent adverse events, i.e., all adverse events occurring between start of treatment and end of the REP [(10 days)]. Adverse events that start before first drug intake and deteriorate under treatment will also be considered as ‘treatment-emergent’.*

For details on the treatment definition, see [Section 6.1](#).

According to ICH E3 (10), in addition to Deaths and serious adverse events, ‘other significant’ AEs need to be listed in the CTR. These will be any non-serious adverse event that led to an action taken with study drug (e.g. dose reduced or interrupted).

An overall summary of AEs will be presented. This overall summary will comprise summary statistics for the class of adverse events of special interest (AESIs).

The following are considered as AESIs:

#### **Section 5.2.6.1 of the CTP:**

*Hepatic injury*

*Patients with cirrhosis: Hepatic injury is defined by the following alterations of hepatic laboratory parameters:*

- *Patients with normal aminotransferases at baseline:*
  1. *ALT and/or AST  $\geq 3 \times ULN$  combined with a) or b) or c)*
    - a) *Total bilirubin  $\geq 2 \times ULN$  at the same visit or within 30 days of each other*
    - b) *INR  $\geq 1.5 \times ULN$  at the same visit or within 30 days of each other*
    - c) *New-onset or worsening of fatigue, nausea, vomiting, right upper quadrant pain or tenderness, fever, rash, eosinophilia ( $> 5\%$ )*
  - OR*
  2. *ALT and/or AST  $\geq 5 \times ULN$*
- *Patients with abnormal ALT, AST, total bilirubin, or INR at baseline:*
  1. *ALT and/or AST  $\geq 2 \times \text{baseline}$  or  $\geq 300 \text{ U/L}$  combined with a) or b) or c)*
    - a) *Total bilirubin  $> 2 \times \text{baseline}$*
    - b) *INR  $> 1.2 \times \text{baseline}$*
    - c) *New-onset or worsening of fatigue, nausea, vomiting, right upper quadrant pain or tenderness, fever, rash, eosinophilia ( $> 5\%$ )*
  - OR*
  2. *ALT and/or AST  $\geq 3 \times \text{baseline}$*

These lab findings constitute a hepatic injury alert. In such instances the testing should be repeated within 48 to 72 hours. If elevations persist, the patients need to be followed up according to the "DILI checklist" provided via eDC. Patients should be followed up until resolution of symptoms or signs in the above stated situations. Patients should also be referred to their hepatologist.

In case of new clinical symptoms of hepatic injury (icterus, unexplained encephalopathy, unexplained coagulopathy, right upper quadrant abdominal pain, etc.) without lab results (ALT, AST, total bilirubin) available, the investigator should make sure these parameters are analysed, if necessary, in an unscheduled blood test. Should the results meet the criteria of hepatic injury alert, the procedures described above should be followed.

For healthy volunteers no AESIs are defined.

The investigator had to classify on the eCRF whether an observed AE was an AESI or not.

The intensity (severity) and the causal relationship of AEs are considered according to **Section 5.2.6.1 of the CTP:**

Intensity (severity) of AEs

The intensity (severity) of adverse events should be classified and recorded in the CRF according to the Common Terminology Criteria for Adverse Events (CTCAE) version 5.0.

Causal relationship of AEs

Medical judgement should be used to determine the relationship between the adverse event and the trial treatment, considering all relevant factors, including pattern of reaction, temporal relationship, de-challenge or re-challenge, confounding factors such as concomitant medication, concomitant diseases, and relevant history.

The frequency of subjects with AEs will be summarised by study group, primary System Organ Class (SOC), and preferred term (PT). Separate tables will be provided for subjects with serious AEs (SAEs), AESIs, drug-related AEs, drug-related SAEs and AE intensity.

The SOCs will be sorted by default alphabetically, PTs will be sorted by frequency (within SOC). The MedDRA version number will be displayed as a footnote in the respective output.

For disclosure of AE data on ClinicalTrials.gov, the frequency of subjects with non-serious AEs occurring with an incidence of greater than 5 % (in preferred terms) will be summarised by treatment, primary SOC and PT. The frequency of subjects with SAEs will also be summarised.

For disclosure of AE data in the EudraCT register, the frequency of AEs, the frequency of non-serious AEs with an incidence of greater than 5 % (in preferred terms) and the frequency of SAEs will be summarised.

In addition, frequencies of subjects with non-serious AEs that had an incidence of > 5% for at least one treatment will be summarised by treatment, primary SOC and PT.

### **7.8.2 Laboratory data**

The analyses of laboratory data will be descriptive in nature and based on BI standards ([11](#)).

Analyses will be based on normalised values, which means transforming to a standard unit and a standard reference range. The original values will be analysed if the transformation into standard unit is not possible for a parameter.

#### **Section 7.2.5 of the CTP:**

*Laboratory data will be analysed both quantitatively as well as qualitatively. The latter will be done via comparison of laboratory data to their reference ranges. Values outside the reference range [will be flagged]. [Study] groups will be compared descriptively with regard to distribution parameters as well as with regard to frequency and percentage of patients with abnormal values or clinically relevant abnormal values.*

Clinically relevant findings in laboratory data will be reported as baseline conditions (prior to administration of study treatment) or as AEs (after administration of study treatment) if judged clinically relevant by the investigator, and will be analysed as such.

Descriptive statistics of laboratory data including change from baseline (see [Section 6.7](#)) will be calculated by planned time point based on the first value of the subject at that planned time point (or assigned to that planned time point). For baseline value, the last measurement before drug administration will be used.

### **7.8.3 Vital signs**

The analyses of vital signs (BP and PR) will be descriptive in nature.

Descriptive statistics of vital signs including change from baseline (see [Section 6.7](#)) will be calculated by planned time point based on the first value of the subject at that planned time point (or assigned to that planned time point). For baseline value, the last measurement before drug administration will be used.

Clinically relevant findings in vital signs will be reported as baseline conditions (prior to administration of study treatment) or as AEs (after administration of study treatment) if judged clinically relevant by the investigator, and will be analysed as such.

[figure not shown]
#### **7.8.4 ECG**

Clinically relevant findings in ECG will be reported as baseline conditions (prior to administration of study treatment) or as AEs (after administration of study treatment) if judged clinically relevant by the investigator, and will be analysed as such. No separate listing or analysis of ECG data will be prepared.

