5.2.4 Electrocardiogram

The 12-lead ECGs (I, II, III, aVR, aVL, aVF, V1 - V6) must be administered by a qualified technologist and results will be recorded as scheduled in the [flow chart](#). To achieve a stable heart rate at rest and to assure high quality recordings, the site personnel will be instructed to assure a relaxed and quiet environment, so that all subjects are at complete rest. The investigator or a designee will evaluate whether the ECG is normal or abnormal and assess clinical relevance. ECGs may be repeated for quality reasons and a repeated recording used for analysis.

All ECGs will be recorded for a 10 sec duration after subjects have rested for at least 5 min in a supine position. ECG assessment will always precede all other study procedures scheduled for the same time to avoid compromising ECG quality. Additional ECGs may be recorded for safety reasons. Dated and signed printouts of ECG with findings should be documented in patient's medical record.

Clinically relevant abnormal findings will be reported either as baseline condition (if identified at the screening visit) or otherwise as AEs and will be followed up and/or treated as medically appropriate.

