5.6 APPROPRIATENESS OF MEASUREMENT

All measurements performed during this trial are standard measurements and will be performed to monitor subjects' safety and to determine pharmacokinetic parameters in an appropriate way. The scheduled measurements will allow monitoring of changes in vital signs, standard laboratory values, and ECG parameters that might occur because of administration of trial medication. The safety assessments are standard, are accepted for evaluation of safety and tolerability of an orally administered drug and are widely used in clinical trials. The pharmacokinetic parameters and measurements outlined in section 5.3.1 are generally used assessments of drug exposure. The biomarkers outlined in sections 5.3.3 and other assessments outlined in section 5.5 are of exploratory nature only.

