7. STATISTICAL METHODS AND DETERMINATION OF SAMPLE SIZE

The main objective of this trial is to investigate the pharmacokinetics of digoxin, furosemide, metformin and rosuvastatin given as a cocktail following oral administration based on the primary pharmacokinetic endpoints, as listed in sections [2.2](#) and section [2.3](#). The trial is designed to allow comparisons between compensated and decompensated F4 graded liver fibrosis (cirrhosis) patients (Child-Pugh A and Child-Pugh B) versus healthy subjects (reference) and will be evaluated statistically by use of a linear model for logarithmically transformed PK endpoints.

A further objective is to evaluate and compare further pharmacokinetic parameters between the treatments. These pharmacokinetic parameters will be assessed by descriptive statistics. Biomarker endpoints will be analyzed by descriptive statistics.

The assessment of safety and tolerability is a further objective of this trial and will be evaluated by descriptive statistics for the parameters specified in section [2.2](#).

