7.2.5 Safety analyses

Adverse events will be coded using the Medical Dictionary for Drug Regulatory Activities (MedDRA). Standard BI summary tables and listings will be produced. All adverse events with an onset between start of treatment and end of the REP, a period of 10 days after trial medication intake, will be assigned to the on-treatment period for evaluation.

All treated patients will be included in the safety analysis. In general, safety analyses will be descriptive in nature and will be based on BI standards. No hypothesis testing is planned.

Statistical analysis and reporting of adverse events will concentrate on treatment-emergent adverse events, i.e., all adverse events occurring between start of treatment and end of the REP. Adverse events that start before first drug intake and deteriorate under treatment will also be considered as 'treatment-emergent'.

Frequency, severity, and causal relationship of adverse events will be tabulated by system organ class and preferred term after coding according to the current version of the Medical Dictionary for Drug Regulatory Activities (MedDRA) at database lock.

Laboratory data will be analysed both quantitatively as well as qualitatively. The latter will be done via comparison of laboratory data to their reference ranges. Values outside the reference range as well as values defined as clinically relevant will be summarised. Treatment groups will be compared descriptively with regard to distribution parameters as well as with regard to frequency and percentage of patients with abnormal values or clinically relevant abnormal values.

Vital signs, physical examinations, or other safety-relevant data observed at screening, baseline, during the trial and at the end-of-trial evaluation will be assessed with regard to possible changes compared to findings before start of treatment.

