#### **4. CHANGES IN THE PLANNED ANALYSIS OF THE STUDY**

All analyses as planned in the CTP will be performed and are described in more detail in this TSAP. The following changes compared to the CTP will be made:

According to the study design, the treatment groups incorrectly referred to in the CTP actually correspond to the study groups. Therefore, only the term “study group” is used in the TSAP and the citations from the CTP were corrected in the TSAP.

Smoking and drinking habits were not assessed in physical examinations as in CTP Section 5.2.5 indicated. So these will not be reported.

In Section 7.2.5 of the CTP, the analysis of laboratory data was stated twice, which could be misleading. Therefore, the citation from the CTP was corrected in the TSAP [Section 7.8.2](#) so that values outside the reference range will be flagged and the laboratory values will be analysed descriptively by study group.

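### 12-lead ECG is a stand-alone safety endpoint, but SAP 7.8.4 gives it no output of its own, and this is neither declared in SAP 4 nor reconciled with the listing rule in SAP 7

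*SAP*

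**What the plan says.** Protocol 2.3.2, repeated in SAP 5.3.3, names four safety endpoints: adverse events (including relevant physical-examination findings), safety laboratory tests, 12-lead ECG, and vital signs.

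On the use of ECG data, the protocol says:

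- Section 5.2.4: the investigator classifies each ECG as normal or abnormal and judges its relevance. "Clinically relevant abnormal findings will be reported either as baseline condition (if identified at the screening visit) or otherwise as AEs". The section also allows a repeat recording to be the one used for analysis.
- Section 5.6: "The scheduled measurements will allow monitoring of changes in vital signs, standard laboratory values, and ECG parameters" that might follow from the trial medication.
- Section 7: safety and tolerability "will be evaluated by descriptive statistics for the parameters specified in section" 2.2. That section holds the pharmacokinetic endpoints; the safety endpoints are in 2.3.2.
- Section 7.2.5: after naming vital signs and physical examinations, it adds that "other safety-relevant data observed at screening, baseline, during the trial and at the end-of-trial evaluation will be assessed with regard to possible changes" from the findings before treatment.

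SAP 7.8.4 says: "Clinically relevant findings in ECG will be reported as baseline conditions (prior to administration of study treatment) or as AEs" after dosing, if the investigator judges them relevant. It then closes the matter: "No separate listing or analysis of ECG data will be prepared".

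SAP 4 says: "All analyses as planned in the CTP will be performed and are described in more detail in this TSAP". It declares three changes: the term study group, smoking and drinking habits, and the laboratory text. ECG is not among them. SAP 7 has a general rule that every subject's individual values go into listings.

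**The concern.** A declared and collected endpoint ends with no result of its own, and a reader comparing the two documents is not told that this was decided. SAP 4 declares something as small as the unreported smoking and drinking habits, so its silence on ECG suggests that nothing changed there.

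The content matters because of digoxin. Protocol 1.2.2 attributes slowing of heart rate and conduction to it. Protocol 3.3.3 excludes subjects on PQ and QTc limits. The trial asks whether cirrhosis alters digoxin exposure. If exposure turns out higher in cirrhosis, the natural next question is whether conduction or repolarisation intervals moved by group. The planned report could answer only through adverse events judged by investigators in an open-label trial.

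**Working it through.** The documents contain no ECG figure to reproduce. The check is mainly a comparison of text, followed by an illustration.

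**Step 1. Endpoint against output.**

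| Safety endpoint (protocol 2.3.2, SAP 5.3.3) | Output planned in the SAP |
|---|---|
| Adverse events, with relevant physical-examination findings | Frequency tables by study group (7.8.1); no separate examination output (7.8.5) |
| Laboratory tests | Descriptive statistics with change from baseline; out-of-range values flagged (7.8.2) |
| 12-lead ECG | None of its own; relevant findings become baseline conditions or adverse events (7.8.4) |
| Vital signs | Descriptive statistics with change from baseline (7.8.3) |

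The endpoint definition folds physical examination into adverse events, so SAP 7.8.5 matches it. ECG is not folded in, yet SAP 7.8.4 treats it in the same way.

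**Step 2. Protocol against SAP.** The adverse-event route in 7.8.4 agrees with protocol 5.2.4. Removing everything else does not sit well with the reference to analysis in 5.2.4, the purpose stated in 5.6, or the descriptive statistics in section 7.

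**Step 3. SAP against itself.** SAP 7 lists individual values, while 7.8.4 prepares no separate ECG listing. SAP 6.7 has adherence to the ECG time windows checked, but the values recorded in those windows are not reported.

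**Step 4. What the adverse-event route can show (illustration on assumed values).** Assume a baseline PQ mean m of 160 to 170 ms, a between-subject SD s of 15 to 20 ms, and a uniform lengthening d of 10 ms. Take 220 ms, the screening limit in protocol 3.3.3, as a stand-in for a relevant value. Truncation of enrolled subjects at that limit is ignored.

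p = 1 − Φ((220 − m − d)/s); P(at least one of n) = 1 − (1 − p)^n

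- m = 160, s = 15: z = 50/15 = 3.33, p = 0.0004. P = 0.8% for n = 18 and 0.3% for n = 6.
- m = 170, s = 20: z = 40/20 = 2.00, p = 0.0228. P = 34% for n = 18 and 13% for n = 6.
- In the second case, with no shift, p = 0.0062 and P is already 10.6% for n = 18. Even a crossing would say little about a shift.

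**Step 5. What a change-from-baseline summary can show.** Assume an SD of change s_d of 8 to 15 ms. The half-width of the 90% interval is t(0.95, n − 1) × s_d/√n. The last column is the probability that the lower limit lies above zero when the true change is +10 ms.

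| n | 90% CI half-width | Lower limit above zero |
|---|---|---|
| 18 (both cirrhosis groups) | 3.3 to 6.2 ms | 86% to >99% |
| 12 (Child-Pugh A) | 4.1 to 7.8 ms | 70% to 99% |
| 6 (Child-Pugh B) | 6.6 to 12.3 ms | 41% to 84% |

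These are within-group changes. The contrast with the healthy group would be less precise.

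**The case against.** The best defence is that SAP 7.8.4 follows the protocol section that governs ECG. Section 5.2.4 sends relevant findings to baseline conditions or adverse events, and the SAP repeats that. Section 7.2.5 does not name ECG and does not prescribe a table. It does name physical examinations, which the SAP also handles by the adverse-event route. Section 5.6 justifies taking measurements and makes no analysis commitment. The promise in section 7 points to a section without safety parameters. All of this stands, and it means that the departure from the protocol is inferred from several passages and contradicts no single explicit instruction. It does not explain why ECG, alone among the three stand-alone measured endpoints, has no output, or why SAP 7 and 7.8.4 differ.

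A reader might infer that any systematic ECG effect would escape notice, or that the SAP abandons ECG altogether. The documents do not support either. Relevant findings reach the adverse-event tables by study group, and SAP 7.8.3 summarises pulse rate against baseline. A reader might also size the gap by the confidence limit for zero events in 6 patients. That limit applies to any binary outcome in the group and says nothing about a mean shift.

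Two facts cannot be checked:

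- **ECG times.** They are blank in the public flow chart. The readable text confirms ECG at screening and at the end-of-trial visit (day 11 to 18), which falls after the 10-day residual effect period. The 15-minute tolerance for ECG in protocol 6.1 suggests timed recordings but does not show when they occur.
- **Stored values.** Section 5.2.4 mentions printouts with findings. No readable text shows that post-dose intervals are held as numbers.

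Finally, protocol 1.2.2 expects no severe cardiovascular effects from the single low dose, so the stakes are modest.

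**Conclusion.** The point holds as a gap in reporting and consistency. A stand-alone, collected safety endpoint has no output of its own. SAP 4 does not say so, and the general listing rule in SAP 7 is left unreconciled. What the report would not show is a sub-clinical group shift in conduction or repolarisation intervals.

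The numerical size rests wholly on the assumed PQ means, SDs and flag limit. On those values the adverse-event route would usually miss a 10 ms shift. A summary of mean change would usually show it in Child-Pugh A or in all cirrhosis patients, and less reliably in the 6 Child-Pugh B patients. That advantage exists only if ECGs were recorded while digoxin was present and the intervals can be retrieved. The point does not touch the primary pharmacokinetic analysis. It is a worthwhile improvement, not a serious flaw.

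**What to change.** Replace the last sentence of SAP 7.8.4 with text to this effect:

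> ECG results will be listed by subject and planned time point. Where intervals are recorded, heart rate, PQ, QRS and QTc will be summarised descriptively by study group as values and change from baseline (Section 6.7). Otherwise the investigator's normal/abnormal evaluation before and after dosing will be tabulated by study group.

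If ECG output is still to be omitted, add that to SAP 4 with a reason, and reconcile it with SAP 5.3.3 and the listing rule in SAP 7.

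The cost is one listing and one table, plus data entry for about 30 subjects (12 + 12 + 6) if intervals exist only on printouts. The result is descriptive and has low precision for the 6 Child-Pugh B patients.

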#### **7.8.5 Physical examination**

Clinically relevant findings in physical examination will be reported as baseline conditions (prior to administration of study treatment) or as AEs (after administration of study treatment) if judged clinically relevant by the investigator, and will be analysed as such. No separate listing or analysis of physical examination data will be prepared.

### **7.9 OTHER ANALYSIS**

#### **7.9.2 Analyte concentration**

The analyte concentrations will be descriptively analysed on the planned sampling times.

##### **Section 7.2 of the CTP:**

*Only concentration values within the validated concentration range and actual sampling times will be used for the calculation of pharmacokinetic parameters. Concentrations used in the pharmacokinetic calculations will be in the same format provided in the bioanalytical report, (that is, to the same number of decimal places provided in the bioanalytical report).*

## **8. TIMEPOINT OF RELEASE OF TREATMENT INFORMATION**

The treatment information will be loaded into the trial database at trial initiation.

